inclusion criteria for phase 1 are (i)  $\geq 55$  years and  $\leq 80$  years old at the time of the visit; (ii) does not already have lung cancer; and (iii) meets 2013 USPSTF smoking criteria for LDCT screening (30+ pack-year smoking history and current smoker or quit in the past 15 years) or may meet the criteria if a complete smoking history were taken. The inclusion criteria for phase 2 are (i)  $\geq 50$  years and  $\leq 80$  years old at the time of the visit; (ii) does not already have lung cancer; and (iii) meets 2021 USPSTF smoking criteria for LDCT screening (20+ pack-year smoking history and current smoker or quit in the past 15 years) or may meet the criteria if a complete smoking history were taken.

*Post-Implementation Provider and Staff Interviews:* Up to 36 providers and staff who participated in the pilot implementation or clinical trial will be included in the interviews.

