### **Aim 3. Evaluation**

*Patient Outcomes Assessment:* up to 21,000 patients will be enrolled. Eligibility criteria are the same as for participation in the pilot implementation and clinical trial.

*Provider and Staff App Usage Assessment:* up to 1,200 providers and staff will be enrolled. Eligibility criteria are the same as for participation in the pilot implementation and clinical trial.

*Provider and Staff Surveys:* Up to 400 providers and staff from University of Utah primary care clinics will be surveyed regarding the intervention. Providers and staff will be eligible if they have interacted with the intervention through the pilot implementation or clinical trial.

*Patient Surveys:* Up to 200 patients from University of Utah primary care clinics will be surveyed regarding the intervention. Patients will be eligible if the intervention was used in their care and they speak English.

*Provider and Staff Focus Groups:* Up to 36 providers and staff will be enrolled in focus groups to evaluate the intervention as well as explore implementation and adoption issues with CDS, SDM, and guideline-focused care in general. Eligibility criteria will be the same as for the provider and staff surveys.

*Patient Focus Groups:* Up to 18 patients will be enrolled in focus groups to evaluate the intervention as well as explore implementation and adoption issues with CDS, SDM, and guideline-focused care in general. Eligibility criteria will be the same as for the patient surveys.

*Stakeholder Interviews:* Up to 100 key stakeholders who implemented the intervention at the University of Utah or elsewhere will be interviewed with a goal of understanding barriers and facilitators to the scalable dissemination of evidence-based CDS, as well as to estimate the associated time and resource costs. Eligibility criteria will be involvement in the implementation of the intervention for clinical care purposes.

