### **Aim 3. Evaluation**

*Patient Outcomes Assessment:* The primary outcome is the proportion of patients eligible for LDCT screening per USPSTF guidelines receiving LDCT screening. Planned secondary outcomes are the expected number of lung cancer deaths prevented given the risk profiles of individuals screened with LDCT, the expected number of major complications given the risk profiles of individuals screened with LDCT, and, if approved by the University of Utah Value Driven Outcomes research committee, the operating margin attributable to study patients during study period (total revenues minus total cost). Data for the operating margin analysis

will leverage the Value Driven Outcomes value analysis tool co-developed by PI [name] to determine the true costs of care.

We will report the number of patients and patient characteristics for each phase of the interrupted time series (ITS) study. We anticipate a 12-month baseline phase, a 9-month intervention phase, and a 9-month enhanced intervention phase which incorporates improvements made to the CDS intervention based on initial experience. We will conduct a segmented regression analysis to fit the monthly series and assess the extent to which the intervention was associated with changes in outcome measures. The study phases constitute three segments of regression models with monthly time points. We will use the segmented least squares approach with parameters for intercept, baseline trend, and changes in the level and trend after the intervention. We will start with assuming a linear trend line within each segment. Nonlinearity trends will be explored if the linear assumption is violated. We will use the Durbin Watson statistic as a measure of autocorrelation and test up to six-order autocorrelation. Potential confounding is limited to covariates associated with the outcome that change at the time of the intervention. We will test for confounding due to changes in study population characteristics such as age, gender and race. Statistical significance will be defined at alpha = 0.05.

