To mitigate the impact of pandemic COVID19, we will make the following two modifications in the statistical analysis plan. First, we will redefine the baseline phase so that it has no overlap with the lockdown period, because all the non-essential medical visits have been cancelled during this period. Secondly, we anticipate the patient characteristics and composition during the intervention phase and even enhanced intervention phase might be different from the baseline phase which is observed before the pandemic. We will compare the distributions of patient characteristics across the three phases of the ITS study. If significant discrepancies are observed in the patient characteristics and composition, we will conduct propensity score modeling and use a matching or weighting approach to create a comparable study cohort in each phase before running the originally proposed segmented regression analysis. If any lock-down periods coincide with the intervention phases, we may remove visits occurring during these periods from the analysis.

To estimate statistical power, we followed Rozario, Moore and McWilliams' approach, and used the statistical software SAS. We assumed the proportion of eligible patients receiving LDCT screening, the primary outcome in the study, will increase from the current 6.4% to at least 12.8% during the intervention phase and 20% during the enhanced intervention phase. Empirical EHR data indicate at least 900 patients per month will meet USPSTF LDCT eligibility criteria throughout the study period. With this conservative monthly sample estimation and the length of time at each phase, we would have more than 95% power to detect

the hypothesized differences in the primary outcomes at different phases. All the estimated statistical powers were calculated based on two-sided tests with a significance level of alpha = 0.05.

*Provider and Staff App Usage Assessment:* Utilization metrics will include the number of clinics, providers, and other empowered staff utilizing the intervention.

*Provider and Staff Surveys:* Descriptive data analysis will be conducted and aggregated data will be compared across groups.

*Patient Surveys:* The same methods will be used as for the provider and staff surveys.

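### The eligibility criteria move from the 2013 to the 2021 USPSTF version between trial phases, and the primary time-series proportion fixes no version, so one level change can mix intervention effect with a change in who is counted

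*Combined protocol and SAP*

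**What the plan says.** The document is a combined protocol and SAP.

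- **Study Population, Inclusion Criteria, Aim 2.** In phase 1 a trial patient is aged 55 to 80 and "meets 2013 USPSTF smoking criteria for LDCT screening (30+ pack-year smoking history and current smoker or quit in the past 15 years". In phase 2 the patient is aged 50 to 80 and "meets 2021 USPSTF smoking criteria for LDCT screening (20+ pack-year smoking history and current smoker or quit in the past 15 years". Both phases also admit a patient who fits "or may meet the criteria if a complete smoking history were taken".
- **Inclusion Criteria, Aim 3, Patient Outcomes Assessment.** "Eligibility criteria are the same as for participation in the pilot implementation and clinical trial".
- **Statistical Methods, Aim 3.** "The primary outcome is the proportion of patients eligible for LDCT screening per USPSTF guidelines receiving LDCT screening". No version or year is attached. "We anticipate a 12-month baseline phase, a 9-month intervention phase, and a 9-month enhanced intervention phase". The segmented model has an intercept, a baseline trend, and level and trend changes, with no term for a criteria change.
- **Safeguards in the same section.** "We will test for confounding due to changes in study population characteristics such as age, gender and race". Under the COVID-19 modifications, "We will compare the distributions of patient characteristics across the three phases of the ITS study". If these differ significantly, propensity matching or weighting comes before the segmented regression.

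Two things are not stated: which criteria apply in the baseline months, and how trial phases 1 and 2 correspond to the baseline, intervention and enhanced segments.

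**The concern.** A level change in an interrupted time series estimates an intervention effect only if the same kind of patient is counted on both sides of the boundary. Here the wider criteria bring in patients aged 50 to 54 and patients with 20 to 29 pack-years. If their screening rate differs from that of patients who met the 2013 criteria, the recorded proportion moves even when nobody's chance of screening has changed. An extra model term would not help, because a criteria change that falls on a segment boundary cannot be separated from that boundary's level change.

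The study is not randomised and the plan describes no control series, so these contrasts carry the evidence on the primary outcome. A real gain could be understated, or an enhancement with no effect could look harmful or beneficial.

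**Working it through.** **Inputs from the documents**
- Planned rates of 6.4%, 12.8% and 20% in the three segments, at least 900 eligible patients per month, two-sided alpha 0.05, power above 95% (Statistical Methods, Aim 3).
- Segments of 12, 9 and 9 months (same section), so the enhanced phase starts at month 22.
- The 2021 criteria enlarge the eligible pool by 67% (Background; a general figure).
- The 6.4% was measured in the year before August 2018 (Background), before the 2021 criteria existed.

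**Assumptions**
- The 67% applies locally.
- 900 per month is the 2013-eligible count.
- The criteria change at month 22, and effects are immediate steps.
- Monthly counts are independent binomial.
- No propensity adjustment has been applied.

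**1. The plan's own power.** The pooled phases hold 12 × 900 = 10,800 and 9 × 900 = 8,100 patients. A two-proportion test gives about 100% power for 6.4% v 12.8% (10,800 v 8,100) and for 12.8% v 20% (8,100 v 8,100). Even one month against one month (900 v 900) gives 99.6% and 98.5%. A six-parameter segmented least-squares fit to simulated 30-month series also gives about 100% for both level changes. The stated power is reproduced for a constant population.

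**2. Recorded rate after the change.** Let p be the rate in 2013-eligible patients, r the rate in the newly eligible, and g the pool growth:

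recorded rate = (p + g × r) / (1 + g)

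With g = 0.67 the newly eligible are 0.67 / 1.67 = 40% of the denominator, and the monthly count becomes 900 × 1.67 = 1,503.

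**3. Newly eligible screened at a fixed fraction of p.** The true gain is 20 − 12.8 = 7.2 points.
- Half the rate, true gain: (20 + 0.67 × 10) / 1.67 = 16.0%, recorded as +3.2 points.
- Half the rate, null enhancement: (12.8 + 0.67 × 6.4) / 1.67 = 10.2%, recorded as −2.6 points.

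The table uses 20,000 simulated series per scenario.

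| r as a share of p | True +7.2 recorded as | Power | Null recorded as | False significant fall |
|---|---|---|---|---|
| 50% | +3.2 | 90% | −2.6 | about 80% |
| 75% | +5.2 | 99.9% | −1.3 | about 31% |
| 90% | +6.4 | about 100% | −0.5 | about 10% |
| 100% | +7.2 | about 100% | 0 | about 4% |

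The last row matches the fixed-population reference: this model gives about 4% significant results in each direction under the null.

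**4. Pessimistic case.** The newly eligible stay at 6.4% while the others rise to 20%: (20 + 0.67 × 6.4) / 1.67 = 14.5%, recorded as +1.7 points, power 47%.

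**5. The opposite direction.** The newly eligible are screened at 20% and the others stay at 12.8%: (12.8 + 0.67 × 20) / 1.67 = 15.7%, a false gain of 2.9 points.

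**6. Smaller pool (g = 0.20, assumed).** At a 6.4% new rate the true gain is recorded as +4.9 points with power above 99%, and a null shows a false fall in about 22% of runs.

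**7. The safeguards.** The confounding test names age, gender and race as examples and states no remedy. Age covers one half of the criteria change and pack-years the other. The propensity step is conditional, lists no covariates, and leaves matching or weighting open. Matching could restrict to the overlapping population if age and pack-years are in the model. Weighting cannot balance patients aged 50 to 54 or with 20 to 29 pack-years against a 2013-criteria segment that has none.

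**The case against.** The strongest reply is that the plan already provides for changes in composition. With 40% of the later denominator new, the propensity step would probably be triggered, so unadjusted figures do not describe the plan carried out in full. This stands as a limit on the figures. It does not remove the point, because whether the adjustment works depends on covariates and a method that are still open.

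A second reply is that the inclusion criteria govern enrolment, while an unversioned outcome definition could be applied with one version throughout. That reading is possible, and admitting patients of uncertain eligibility does show that enrolment and denominator differ. But the outcomes assessment is expressly given the trial's eligibility, so the more direct reading is a population that changes.

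Third, the 6.4% case gives newly eligible patients no benefit from a tool and prompts that they also receive. That is fair, and it should not be the headline.

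A reader might infer that the trial cannot detect its planned gain, or that the stated power is wrong. The documents support neither. The power reproduces on its own inputs, and in the milder cases it stays at 90% or more. A reader might also take the start of the enhanced phase as the stated switch point. That is an inference from the 9-month timing of the improvement release; if the switch falls elsewhere, a different contrast is affected. Finally, the anticipated smoking-history prompt might seem to shift the denominator as well. It is only one of several possible enhancements and the documents give no figure for it, so nothing here rests on it.

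**Conclusion.** The concern holds as a defect in the definition of the primary series. As written, the counted population changes between trial phases, and the level change at that boundary mixes intervention effect with a change in who is counted. The planned safeguards may reduce this but do not ensure it.

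Under the stated assumptions and before propensity adjustment, the clearest risk is a false finding when the enhancement has no effect: about 10% to 80% of runs show a significant fall when newly eligible patients are screened at 90% down to 50% of the others' rate, against about 4% in a fixed population. Loss of power is serious only in more extreme cases. The bias is zero if the two groups are screened at the same rate, and it reverses if the newly eligible are screened more often. The local pool growth and the newly eligible patients' screening rate are not in the documents, so neither direction nor size can be settled from them. This should be corrected before the analysis is run.

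**What to change.** 1. Map trial phases 1 and 2 to the three time-series segments, give the date of the criteria change, and state the baseline criteria.
2. Define the primary series on one named criteria version in all months. The 2013 version matches the period of the 6.4% baseline and nests within the 2021 version. The 2021 version applied to every month, baseline included, is also acceptable. Use the other version as a sensitivity analysis.
3. Report patients eligible only under the 2021 version as a separate series.
4. Reconcile the 55 to 80 age range given for the anticipated smoking-history prompt (Procedures, Aim 2) with the 50 to 80 range for phase 2 (Inclusion Criteria, Aim 2).

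The cost is SAP wording plus some data work: a criteria-version flag per patient-month, and extraction of 2021-only patients in the earlier months. With 2013 fixed, the plan's power inputs apply unchanged, so nothing is lost against its own calculation. The drawback of that choice is that newly eligible patients, who are part of the phase 2 target population, leave the primary series.

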### **Aim 3. Evaluation**

*Patient Outcomes Assessment:* up to 21,000 patients will be enrolled. Eligibility criteria are the same as for participation in the pilot implementation and clinical trial.

*Provider and Staff App Usage Assessment:* up to 1,200 providers and staff will be enrolled. Eligibility criteria are the same as for participation in the pilot implementation and clinical trial.

*Provider and Staff Surveys:* Up to 400 providers and staff from University of Utah primary care clinics will be surveyed regarding the intervention. Providers and staff will be eligible if they have interacted with the intervention through the pilot implementation or clinical trial.

*Patient Surveys:* Up to 200 patients from University of Utah primary care clinics will be surveyed regarding the intervention. Patients will be eligible if the intervention was used in their care and they speak English.

*Provider and Staff Focus Groups:* Up to 36 providers and staff will be enrolled in focus groups to evaluate the intervention as well as explore implementation and adoption issues with CDS, SDM, and guideline-focused care in general. Eligibility criteria will be the same as for the provider and staff surveys.

*Patient Focus Groups:* Up to 18 patients will be enrolled in focus groups to evaluate the intervention as well as explore implementation and adoption issues with CDS, SDM, and guideline-focused care in general. Eligibility criteria will be the same as for the patient surveys.

*Stakeholder Interviews:* Up to 100 key stakeholders who implemented the intervention at the University of Utah or elsewhere will be interviewed with a goal of understanding barriers and facilitators to the scalable dissemination of evidence-based CDS, as well as to estimate the associated time and resource costs. Eligibility criteria will be involvement in the implementation of the intervention for clinical care purposes.

#### **Exclusion Criteria:**

None.

## **Design**

---

Prospective Biomedical Intervention or Experiment

## **Study Procedures**

---

#### **Recruitment/Participant Identification Process:**

##### **Aim 1. Design**

*Pre-Implementation Provider and Staff Interviews:* We will recruit participants in-person or via email in consultation with [name], who oversees research and informatics for the University of Utah Community Physicians Group, and who is a co-investigator on the project. Recruitment may also take place during staff meetings or short educational presentations at clinic sites by [name], other research staff or other clinic directors.

##### **Aim 2. Implementation**

*Provider and Staff Participation in Pilot Implementation and Clinical Trial:* Because the intervention is promoting standard of care, we will base our approach on how University of

Utah Health operationally introduces other health IT interventions to promote standard of care. The PI is Associate Chief Medical Information Officer for the health system and routinely introduces similar interventions for operational purposes outside of a research context. We will follow this usual process, including seeking approval from relevant governance groups such as the Community Physical Group Medical Directors or the EHR Operations committee. We will seek a waiver of informed consent for individual providers and staff as described later.

*Patient Participation in Pilot Implementation and Clinical Trial:* We will seek a waiver of informed consent for targeted patients as described later.

*Post-Implementation Provider and Staff Interviews:* We will use the same recruitment strategies as for Aim 1.

### **Aim 3. Evaluation**

*Patient Outcomes Assessment:* The recruitment approach will be the same as for the patient participation in the pilot implementation and clinical trial as described above.

*Provider and Staff App Usage Assessment:* The recruitment approach will be the same as for the provider and staff participation in the pilot implementation and clinical trial as described above.

*Provider and Staff Surveys:* Survey study participants will be recruited via email. To improve the response rate, we may send up to three reminders. Additionally, we may recruit through targeted in-person distribution of the surveys by research team members.

*Patient Surveys:* Survey study participants will be recruited electronically or via postal mail.

*Provider and Staff Focus Groups:* We will ask in the surveys above if participants are potentially interested in the focus groups. We will recruit from those respondents who answer positively to this question. If needed, additional participants will be recruited in-person or via email.

*Patient Focus Groups:* We will ask in the surveys above if participants are potentially interested in the focus groups. We will recruit from those respondents who answer positively to this question.

*Stakeholder Interviews:* We will recruit participants via email.

*Data Quality Assurance:* Because the intervention is promoting standard of care, we will base our approach on how University of Utah Health operationally introduces other health IT interventions to promote standard of care. As part of standard quality assurance procedures, we will assess smoking history and comorbidities data for all adults who had an outpatient visit in University of Utah Health primary care clinic.

**Informed Consent:**

**Description of location(s) where consent will be obtained:**

For interviews and focus groups, verbal consent will be obtained where the interviews and focus groups are conducted, which are expected to be at the clinics. For surveys, proceeding with the survey will constitute consent. This is expected to take place at the clinics or at the respondents' homes.

**Description of the consent process(es), including the timing of consent:**

Aim 1. Design Pre-Implementation Provider and Staff Interviews: Oral informed consent will be obtained at the beginning of the interview process following participant review of a Consent Cover Letter. See item 8 for details. Aim 2. Implementation Provider and Staff Participation in Pilot Implementation: For the pilot implementation, a waiver of informed consent is sought following assent of the pilot users or the clinical leadership (see Waiver request). Patient Participation in Pilot Implementation: A waiver of informed consent is sought following assent of the pilot users or the clinical leadership (see Waiver request). Provider and Staff Participation in Clinical Trial: A waiver of informed consent is sought following assent of the clinical leadership (see Waiver request). Patient Participation in Clinical Trial: A waiver of informed consent is sought following assent of the clinical leadership (see Waiver request). Post-Implementation Provider and Staff Interviews: For provider and staff interviews, verbal informed consent will be obtained at the beginning of the interview process. Aim 3. Evaluation Patient Outcomes Assessment: A waiver of informed consent is sought as for the Patient Participation in the Pilot Implementation and Clinical Trial. Provider and Staff App Usage Assessment: A waiver of informed consent is sought as for the Provider and Staff Participation in the Pilot Implementation and Clinical Trial. Provider and Staff Surveys: Electronic informed consent will be obtained at the beginning of the survey. See item 8 for details. Patient Surveys: Proceeding with the survey will constitute consent. See item 8 for details. Provider and Staff Focus Groups: Oral informed consent will be obtained at the beginning of the focus groups following participant review of a Consent Cover Letter. See

item 8 for details. Patient Focus Groups: Oral informed consent will be obtained at the beginning of the focus groups following participant review of a Consent Cover Letter. See item 8 for details. Stakeholder Interviews: Oral informed consent will be obtained at the beginning of the interviews following participant review of a Consent Cover Letter. See item 8 for details.

